3.2. Theory of Change

[figure not shown]

Figure 1: Theory of Change (ToC)

The Theory of Change relies on the following key assumptions:

1. LAs hold all data required by OneView, and a sufficient range of data to allow Xantura to run and deliver a predictive model with meaningful predictive value
2. LAs hold telephone contact information for individuals in identified households, and this information is accurate
3. Contacted individuals can and will answer the telephone, and are able to conduct a long enough call to complete the assessment (in one or across multiple calls)
4. Services that address the needs of the individuals in identified households and can aid in preventing homelessness are available
5. Signposted services have capacity (in addition to BAU workload) to provide meaningful support to individuals in identified households
6. Intervening 3-6 months 'upstream' is early enough to prevent (some) cases of homelessness

The intervention is expected to inform households that they are at risk and refer them to support services that they might need, which (if effective) will also lead to a reduction in homelessness applications (Assumptions 4 and 5 of the ToC).

The causal chain requires households to engage with the services offered by the LA, and for these services to effectively address their needs and reduce household risk of homelessness (Figure 2).

Figure 2: Causal chain for impact on homelessness

Any difference in outcomes between the intervention and control groups is the result of the combination of these two components, engagement and effectiveness. The intervention aims to increase engagement with services; we assume that the effectiveness of these services at reducing household risk of homelessness is constant across intervention and control. Therefore, if we find a difference between intervention and control that will imply that the intervention is effective at increasing engagement with services.

However, if we find a null result, the lack of detectable effect could be because the intervention did not increase engagement with services and/or because the services fail to effectively reduce homelessness. The latter would suggest that LA services need improvement for this intervention to be effective. Whilst these two components (engagement and effectiveness of services) are not measured separately in the

impact evaluation, in the event of a null, the results of the IPE will help us understand which of these options is more plausible.

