One intervention that has been piloted in some LAs is a proactive phone call, offering relevant support to a target population. Two LAs have used predictive models to identify households and then had council staff proactively call those households to offer support.

The London Borough of Barking and Dagenham used routine data to target households for phone calls to encourage Council Tax debt repayment (Local Government Association, 2022). The council made proactive calls to residents at summons stage for Council Tax arrears to see if they could set up a payment plan or needed support, using the OneView data platform to target people who looked as though they would be able to afford a payment plan: 210 residents were targeted, 68 could be reached, and 30 set up a repayment plan. The households that were targeted were 50% more likely to have made a payment or set up a payment plan than a similar group of residents that the council did not attempt to call. However, this was not a trial – we do not have information on how the residents were allocated to groups or whether the allocation was random – and there was no statistical analysis of the findings.

Maidstone Borough Council used routine data to target households at risk of homelessness for phone calls that offered preventive support (Merritt and Davies, 2023). In 2019, they worked with the technology company Xantura to develop a predictive analytics tool using the OneView platform, which brings together council data from different areas to predict those at risk of homelessness within the next three to six months. An initial pilot identified 650 households at risk of homelessness and allowed council officers to access a case summary in the OneView platform for

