5.2. Study Design

Study design details

The IE is a two-arm parallel RCT with randomisation at the household level, blocked by LA and predicted risk of homelessness. Households in the 'treatment' arm will receive proactive support (in the form of a phone call) from their LA in addition to BAU support. Households in the 'control' arm will only receive BAU support from LAs. This varies between LAs and refers to the range of activities that LAs and local organisations (including the third sector) undertake, and services they offer, to prevent and reduce homelessness. This support is available to households in both

the intervention and control arms, the difference is whether they receive a phone call that signposts them to the relevant support for them.

Allocation

Verian will randomly allocate households into the trial's two arms with equal probability, with a blocking design to ensure that the sample within each LA is as well balanced as possible on predicted risk of homelessness at the trial's start.

To assign blocks, we will independently sort each LA's sample by a continuous risk score generated by Xantura and then sequentially allocate households to blocks of four, following the sorted order. The target sample size at this point will be a multiple of four, so all blocks should be fully filled. If this is not the case, any remaining households will be entered into the final block. Once sorted into blocks, we will randomly assign households within each block so that every block of four contains two treatment households and two control. If the final block contains an odd number of households, we will randomise those households freely. The sample is thus stratified by LA and then risk score within LA.

We will randomise using the R package 'randomizr' (Coppock, 2019). One researcher will conduct the randomisation, but the code will be checked by another researcher to ensure it has been conducted correctly and can be reproduced. Once conducted, the randomisation code will be saved and made available in the OSF pre-registration that will be published for this trial.

Batching

We will deliver the sample to LAs in three batches, at the start of the first, second, and third months of the trial. We will run the randomisation separately for each batch, using up-to-date risk scores generated by Xantura.

Update to protocol: Study design in Test Valley

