9. SAMPLE SIZE AND POWER CALCULATION

9.1. Sample Size / Power Calculation

There is little evidence at present for the likely scale of any treatment effects, or for the distribution of baseline risk scores in each participating LA or how well they really predict future homelessness. Each of these could impact power. Furthermore, the sample size is limited by the number of at-risk households in the population and LAs' capacity to deliver the treatment, of which we expect the latter to be more limiting. We therefore start here from the planned sample size that LAs initially consented to when they agreed to take part (500 per LA) and consider the implications of various scenarios in which the achieved sample is lower than planned due to delivery constraints or attrition (e.g., missing data), under a set of conservative assumptions.

We present below the Minimum Detectable Effect Size (MDES) for effect of treatment on the (binary) primary outcome measure under each scenario. MDES are shown as absolute percentage point differences, provided as ranges because they vary depending on baseline proportions. To minimise the risk that our power calculations overstate power, we make the conservative assumption that the planned baseline covariates do not account for any variance in the primary outcome. This is in practice unlikely to be the case, although they may not greatly improve power if baseline risk scores are high in most sampled households.

Under our assumed likely scenario, our MDES at alpha = 0.05 and power (beta) = 0.8 is a 2-7 absolute percentage point difference in the proportion of households becoming homeless between treatment and control. Ranges are provided because the MDES expressed in absolute terms varies with base probability of homelessness under the null hypothesis (Figure 3).

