9.3. Software

[figure not shown]
Power calculations were carried out using the [pwrss](#) package in R statistical software.

Table 7: Sample size calculations

		Scenario A	Scenario B	Scenario C	Scenario D
Minimum Detectable Effect Size (MDES) (pp = percentage points)		2-7pp	2-7pp	2-7pp	3-8pp
Alpha		0.05	0.05	0.05	0.05
Power		0.8	0.8	0.8	0.8
Alternative hypothesis: One-sided or two-sided		Two-sided	Two-sided	Two-sided	Two-sided
Number of households	Treatment	1,250	1,085	1,000	868
	Control	1,250	1,085	1,000	868
	Total	2,500	2,170	2,000	1,736
Expected attrition	%	20	20	20	20

Effective sample (Households)	Total	2,000	1,736	1,600	1,388 ²
----------------------------------	-------	-------	-------	-------	--------------------

Figure 3: Scenario C MDES at different levels of homelessness³

² This value is rounded down.

³ Note that we would not expect to see fewer than 50% of households identified by Xantura's predictive model becoming homeless if Xantura's model works as stated.

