10.3. Primary Analyses

Analytical approach

The primary analysis will estimate the effect of treatment on the likelihood of a successful homelessness application being submitted by or on behalf of any individual within a sampled household, on an intent-to-treat (ITT) basis. We plan to apply a parsimonious model with treatment as the predictor of interest, and two baseline covariates used in the blocking design of the randomisation.

The analysis will take the form of a generalised linear model with a logit link function to accommodate the binary measure used for the primary outcome. To improve power, we will cluster standard errors at the block level.

The model will follow this specification:

$$\text{logit}(p(Y_i = 1)) = \beta_0 + \beta_1 \text{Treat}_i + \beta_2 \text{Risk}_i + \beta_3 \text{LA}_i$$

Where:

- $p(Y_i = 1)$ is the probability that the i^{th} household ($i = 1, \dots, n$, where n is the number of households) submitted a successful homelessness application (or had one submitted on their behalf) during the trial period,
- $Treat_i$ is a binary variable for treatment allocation (0 = Control, 1 = Intervention),
- $Risk_i$ is the continuous risk score generated for that household that was used in the pre-trial randomisation,
- LA_i is a vector of binary dummy variables representing the Local Authority the household is in (0 = non-member, 1 = block member).

This approach to the primary analysis cleanly reflects the study's design to maximise power without conditioning on additional covariates that could complicate the interpretation of the model's results. Alternative approaches would be to explicitly represent the blocking design through a vector of dummy variables (instead of separate indicators for risk and LA) in a conditional logistic regression or to drop all covariates and use treatment as the sole predictor. We will follow both of these approaches as sensitivity analyses.

We will report uncertainty through confidence intervals at p-values. For the treatment effect, we will report p-values continuously as well as a binary indication of whether the treatment effect is statistically significant.

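### Section 3.2 explains a null primary result only by failed engagement or failed services, and leaves out a real effect missed through chance or limited power

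*Protocol*

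**What the plan says.** Section 3.2 of the Protocol (Theory of Change) describes a two-link chain: the call raises engagement with services, and the services lower the risk of homelessness. It then explains a null: "if we find a null result, the lack of detectable effect could be because the intervention did not increase engagement with services and/or because" LA support is not effective. For the second case it adds that LA services would need improving. It closes by saying that "in the event of a null, the results of the IPE will help us understand which of these options is more plausible".

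Section 10.3 commits to confidence intervals and continuous p-values, together with "a binary indication of whether the treatment effect is statistically significant". Section 9.1 states that "our MDES at alpha = 0.05 and power (beta) = 0.8 is a 2-7 absolute percentage point difference", and section 9.1 also admits that little is known about the likely size of any effect. Footnote 3 in section 9.3 says "we would not expect to see fewer than 50% of households identified by Xantura's predictive model becoming homeless" if the model works as stated. Section 3.1 warns that households without a phone number lower the chance of finding an effect by intention to treat. None of this is carried into section 3.2.

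**The concern.** A non-significant difference has three possible sources: the call did not change engagement, the services do not work, or there was a real effect that the trial did not detect. Section 3.2 names the first two and sends the IPE to weigh one against the other. Interviews and call records can inform that comparison, but they cannot show whether the null was a false negative.

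A report that followed the text could therefore tell LAs that their calls or their services fail when the data are also compatible with a useful reduction. The risk grew when section 5.2 removed Test Valley from the primary analysis, because the sample then falls below every scenario in Table 7.

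**Working it through.** **Inputs from the Protocol.** Two-sided alpha 0.05 and power 0.80 (section 9.1, Table 7); allocation "with equal probability, with a blocking design" (section 5.2); 500 households per LA and 20% attrition (sections 9.1 and 9.2); covariates assumed to explain no outcome variance (section 9.1).
- Scenario C, named in 9.2 as the expected main scenario: 4 × 500 × 0.80 = 1,600 analysed, n = 800 per arm.
- Without Test Valley: 3 × 500 × 0.80 = 1,200 analysed, n = 600 per arm. This figure is derived here and is not in the Protocol.

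**Assumptions made here.** A true reduction d of 5 percentage points. Control rates p1 from 20% to 90%, because the Protocol fixes none.

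**Formulas.** With p2 = p1 − d and p̄ = (p1 + p2)/2:
- s0 = √[2p̄(1 − p̄)/n] and s1 = √[(p1(1 − p1) + p2(1 − p2))/n]
- the minimum detectable effect (MDES) is the d that solves d = 1.96·s0 + 0.842·s1
- miss rate = 1 − Φ[(d − 1.96·s0)/s1]

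**Reproducing the Protocol's figure.** For n = 800, the MDES is 6.98 points at a 50% control rate and about 1.95 to 1.97 points at 99% or 3%. That is the stated 2–7 points. For n = 600 it is 8.05 points at a 50% control rate.

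**Miss rate, worked at p1 = 50%, p2 = 45%.**
- n = 800: s0 = 0.02497, s1 = 0.02494; (0.05 − 0.04894)/0.02494 = 0.043; miss rate 48.3%.
- n = 600: s0 = 0.02883, s1 = 0.02880; (0.05 − 0.05651)/0.02880 = −0.226; miss rate 58.9%.

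**Over control rates, true reduction 5 points:**

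| Control rate | 1,600 analysed | 1,200 analysed |
|---|---|---|
| 20% | 25.0% | 37.5% |
| 50% | 48.3% | 58.9% |
| 70% | 43.0% | 54.4% |
| 80% | 33.2% | 45.5% |
| 90% | 14.3% | 25.4% |

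**What a null interval would look like.** With 50% in both arms, the 95% half-width is 1.96 × √(2 × 0.25/n): 4.9 points for n = 800 and 5.7 points for n = 600. With 1,200 analysed, even an observed difference of exactly zero would leave a 5-point reduction inside the interval.

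**The case against.** Section 3.2 is Theory of Change narrative rather than an analysis rule. It says what a null could be due to, speaks of a lack of detectable effect, and asks the IPE only to help. A reader might infer that the Protocol binds the evaluators to read non-significance as no effect. The wording does not go that far. What stands is that the list holds only two options and the IPE is pointed at those two.

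Safeguards do exist elsewhere: confidence intervals and continuous p-values in 10.3, the MDES in section 9, the complier analysis in 10.6, and the use of the impact confidence interval in the economic sensitivity analysis (12.2). It would be wrong to say that the Protocol ignores uncertainty. These elements are simply not linked to the reading of a null.

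A reader might also infer a miss rate of 50–60% whatever the control rate. That holds only near 40–60%, and its upper end needs the 1,200-household sample. The 50% in footnote 3 is a floor if the model works, and section 6.2 favours the highest scores, so higher rates with lower miss rates are plausible. At 800 per arm the MDES falls to 5.9 points at 80% and 4.6 at 90%. No covariate gain and 20% attrition are also assumptions that the Protocol itself calls conservative.

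A stronger figure could be built from the Barking and Dagenham exercise in section 1.1, where "210 residents were targeted, 68 could be reached, and 30 set up a repayment plan": 68/210 = 32%, which would dilute a 10-point effect among those reached to 3.2 points. The documents do not support carrying that rate over. It comes from a non-randomised Council Tax exercise, whereas this trial plans a pre-notification text and three to five re-contacts. Failure to reach households also arguably belongs under the first explanation, no added engagement.

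Finally, an interpretation rule could be left to a statistical analysis plan. Here, though, the Protocol itself states the explanations and does so incompletely.

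**Conclusion.** The point holds in a limited form. Section 3.2 gives an incomplete account of a null, and no planned quantity is used to tell an uninformative null from an informative one. For an assumed 5-point reduction, the chance of a false negative runs from 14% to 48% with 1,600 analysed and from 25% to 59% with 1,200, over control rates of 20%, 50%, 70%, 80% and 90%. It is highest at 50%.

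These figures rest on the Protocol's assumptions of two-sided 0.05, no covariate gain and 20% attrition, on full recruitment of 500 per LA, and on the 5 points chosen here. The omission itself does not depend on any one of them.

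**What to change.** In section 3.2, add chance or insufficient power as a third explanation of a null. In section 10.3, report the treatment effect as a percentage-point difference with a 95% confidence interval, standardised from the fitted logistic model, and state how a non-significant result will be read:
- If the interval excludes a stated minimum worthwhile reduction, conclude that there was no worthwhile effect, and use the IPE to separate engagement from service effectiveness.
- If the interval includes it, call the result inconclusive and attribute it to neither.

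The threshold must be fixed before outcome data are seen. The break-even benchmark in section 12.2 is one possible basis, but it needs LA cost data, and section 12.3 still gives the distribution date of the cost form as to be confirmed. If it cannot be set in time, use the MDES for the sample actually analysed.

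The cost is a few sentences and one extra estimate from a model already planned, with no new data. The downside is that a null may have to be reported as inconclusive.

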3.3. Intervention Dates

The intervention will be delivered to participants over a three-month period beginning in early May 2025.

4. STUDY TIMELINE

Table 5: Study Timeline

Staff responsible/ leading	Activity	Dates
Xantura	Implementation of OneView platform and setup of predictive model	August – December 2024
Verian ([name])	Evaluation Design	August – December 2024
Verian ([name])	Scoping qualitative fieldwork with Local Authority staff and stakeholders	January – April 2025
Xantura	Data pull and predictive model run. Results shared with Verian for randomisation and then with LAs	Batch 1: April 2025 Batch 2: May 2025 Batch 3: June 2025
Local Authorities	LAs call identified households in the treatment group	Batch 1: May 2025 Batch 2: June 2025 Batch 3: July 2025
Verian ([name])	Qualitative fieldwork with project beneficiaries and residents	June – November 2025
Xantura	Secondary outcome data pulls (shared with Verian)	Batch 1: August 2025 Batch 2: September 2025 Batch 3: October 2025
Xantura	Primary outcome data pulls (shared with Verian)	Batch 1: February 2026 Batch 2: March 2026 Batch 3: April 2026
Verian ([name])	Analysis and reporting	May – October 2026
Verian ([name])	Final report publication	September 2026

5. IMPACT EVALUATION (IE)

5.1. Aims, Objectives and Hypotheses

Aims and Objectives

The IE aims to estimate the impact of LAs delivering proactive support to households deemed at risk of homelessness in the next 3-6 months on whether they are owed a relief duty.

The **primary objective** of the IE is to estimate the impact of treatment on whether households are owed a relief duty at a 9-month follow-up.

The **secondary objective** is to estimate the impact of treatment on support provided for at-risk households before the 9-month follow-up.

Research hypotheses

The **primary research hypothesis** is that allocation to treatment will reduce the likelihood of a household making a homelessness application that results in them being owed a relief duty at any point between the trial's start and the 9-month follow-up, compared to a business-as-usual (BAU) control. See 'Primary Outcome', below for the operational definition used in this trial.

The **secondary research hypotheses** are that allocation to treatment will increase the likelihood of anyone in the household being issued the following support before the 9-month follow-up:

1. A prevention duty ('Primary Outcome', below)
2. An agreed reduction in Council Tax
3. A discretionary housing payment

The trial will also consider impact on these three secondary outcomes at an earlier 2-month follow-up.

5.2. Study Design

Study design details

The IE is a two-arm parallel RCT with randomisation at the household level, blocked by LA and predicted risk of homelessness. Households in the 'treatment' arm will receive proactive support (in the form of a phone call) from their LA in addition to BAU support. Households in the 'control' arm will only receive BAU support from LAs. This varies between LAs and refers to the range of activities that LAs and local organisations (including the third sector) undertake, and services they offer, to prevent and reduce homelessness. This support is available to households in both

the intervention and control arms, the difference is whether they receive a phone call that signposts them to the relevant support for them.

Allocation

Verian will randomly allocate households into the trial's two arms with equal probability, with a blocking design to ensure that the sample within each LA is as well balanced as possible on predicted risk of homelessness at the trial's start.

To assign blocks, we will independently sort each LA's sample by a continuous risk score generated by Xantura and then sequentially allocate households to blocks of four, following the sorted order. The target sample size at this point will be a multiple of four, so all blocks should be fully filled. If this is not the case, any remaining households will be entered into the final block. Once sorted into blocks, we will randomly assign households within each block so that every block of four contains two treatment households and two control. If the final block contains an odd number of households, we will randomise those households freely. The sample is thus stratified by LA and then risk score within LA.

We will randomise using the R package 'randomizr' (Coppock, 2019). One researcher will conduct the randomisation, but the code will be checked by another researcher to ensure it has been conducted correctly and can be reproduced. Once conducted, the randomisation code will be saved and made available in the OSF pre-registration that will be published for this trial.

Batching

We will deliver the sample to LAs in three batches, at the start of the first, second, and third months of the trial. We will run the randomisation separately for each batch, using up-to-date risk scores generated by Xantura.

Update to protocol: Study design in Test Valley

One of the participating LAs, Test Valley, was unable to supply housing association rent arrears data, which was a key predictor in the predictive risk model. This became apparent after the originally registered version of this protocol was signed off but before any batches had been drawn for Test Valley. Therefore, Xantura developed a simplified set of criteria for identifying and sampling eligible households:

Firstly, Xantura applied a series of **inclusion criteria** for a household in Test Valley to be considered:

- Total debt (across Council Tax and Housing Benefit Overpayment (HBOP)) \geq £1000.
- Total debt \leq £8000, as households exceeding this debt threshold are commonly already known to the authorities or are refusing to collaborate.

- Current debt trend is 'Debt Increase', indicating an accelerating increase in debts over a sustained period.
- Xantura's Risk Framework metric of financial resilience is rated as 'low' or 'medium', meaning the household has low historic evidence or means of recovering from debts.
- No Discretionary Housing Payments in past 6 months.
- No homelessness duty in past 6 months.

Then, Xantura **sorted eligible Test Valley households into tiers** intended to reflect risk of homelessness. The 'highest risk' households (Tier 1) are those with rising debts for both Council Tax and HBOP, and either total debt exceeding £3,000 or evidence of homelessness in the past 18 months. The 'high risk' (Tier 2) households are those with evidence of historic homelessness alongside either rising Council Tax debt or rising HBOP debt (but not both). Lastly, 'moderate risk' households had either rising Council Tax debt or rising HBOP debt (again, not both), but with no evidence of prior homelessness.

Xantura **sampled households** for each cohort beginning with those in Tier 1. If there were not enough households in Tier 1 to meet the target sample size then they selected from Tier 2, and then from Tier 3 if necessary.

In light of these changes, we agreed the following amendments to the evaluation with CHI and Xantura:

1. Xantura will identify eligible households in Test Valley according to a simplified set of criteria rather than the predicted risk scores used in the other LAs.
2. We will randomise households in Test Valley without blocking by risk scores, which would not be available for those households. Those randomised into the intervention will receive support as specified in Section 3.
3. We will exclude Test Valley from any of the pre-registered analyses that make use of predicted risk scores or blocks assigned by risk scores, i.e. the Primary and Secondary Analyses.
4. We will use the pre-registered sensitivity analysis that does not include predicted risk score as a covariate to gauge the impact of the intervention in Test Valley. These will be run with and without Test Valley.
5. We will report estimates of impact from that analysis across the participating LAs to provide indicative evidence of how the planned approach using Xantura's predictive risk scores compares to the 'rules-based approach' taken in Test Valley. We must note that this is a strictly exploratory comparison, and it will not account for other differences between the LAs which might plausibly have driven differences in the efficacy of the intervention.

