9.2. Attrition Assumptions

We conducted power calculations prior to confirmation of the final list of participating councils. When doing this, we considered the following scenarios:

Scenario A (our planned main scenario) – Five LAs take part; 500 households recruited and randomised per LA, with 20% lost as post-randomisation attrition. Achieved n = 2,000.

Scenario B – as Scenario A, but the recruited sample in Batches 2 and 3 are reduced by 20% due to delivery constraints that become apparent in Batch 1. Achieved n = 1,736.

Scenario C – as Scenario A but one of the five LAs withdraws before the start of the trial. Achieved n = 1,600.

RBKC withdrew before the start of the trial (December 2024), so Scenario C will represent the expected main scenario at the time this protocol is first registered.

Scenario D – as Scenario B but one of the five LAs withdraws before the start of the trial. Achieved n = 1,388.

The attrition assumption covers participants opting their data out of the evaluation, gaps in administrative records, or participants moving out of the LA during the trial period. We expect such instances to be few, so the figure of 20% is likely to be conservative. It was arrived at by CHI early in the trial's development and has been maintained in the absence of strong evidence justifying amending it. Note that its impact is minor – adjusting assumed attrition in Scenario A from 20% to 5% changes the range of MDES from 2-7pp to 2-6pp.

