10. ANALYTICAL STRATEGY

10.1. Analytic Sample

The analytic sample will be all households entered into the randomisation for whom the primary outcome is available.

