12.3. Data Collection and Processing

Data Sources

We will collect data on the intervention costs from the LAs through a Cost Data Submission Tool and triangulate these – where relevant and applicable – with appropriate external data sources. The study's impact evaluation will provide estimates of the number of beneficiary households (households whose members avoid being owed a relief duty because they have become homeless) required for the estimation of cost savings resulting from the intervention.

Data Collection Procedures

A Cost Data Submission Tool in the format of an Excel file will be developed by Simetrica-Jacobs. This will be distributed to the LAs participating in the project as part of the IPE's qualitative data collection process (TBC).

The cost estimates obtained from returned submissions forms will be scaled up in line with the project target population in each LA to represent the whole project.

Data Collection Schedule

- Cost data submission form developed – 30th September 2024 (Simetrica-Jacobs)
- Cost data submission form sign-off – 30th October 2024 (CHI/consultation with LAs - TBC)
- Cost data submission form distribution – TBC

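### The stated 2–7pp MDES is for four LAs, but version 3.0 runs the primary analysis on three, where it is about 8pp at a 50% base rate

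*Protocol*

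**What the plan says.** Section 5.2 explains that Test Valley could not supply a key input to the risk model, so its households have no risk score and were not blocked on one. Item 3 of the agreed amendments follows from this: "We will exclude Test Valley from any of the pre-registered analyses that make use of predicted risk scores or blocks assigned by risk scores", and it names the primary and secondary analyses. The primary model in section 10.3 contains the risk score, so it can be fitted only in Barking and Dagenham, Newham and Stockport. Test Valley enters the treatment-only sensitivity analysis (section 10.6) and some exploratory models (section 10.7).

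Section 9.1 still says: "Under our assumed likely scenario, our MDES at alpha = 0.05 and power (beta) = 0.8 is a 2-7 absolute percentage point difference". Section 9.2 identifies the scenario: after one of five LAs withdrew, "Scenario C will represent the expected main scenario at the time this protocol is first registered". Table 7 gives Scenario C as 2,000 randomised, 1,600 effective and 2–7pp. The smallest scenario, D, has 1,388 effective households and 3–8pp. No scenario has three LAs.

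On the base rate, the footnote to Figure 3 says: "Note that we would not expect to see fewer than 50% of households identified" becoming homeless, provided the risk model works as claimed.

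Section 10.1 says: "The analytic sample will be all households entered into the randomisation for whom the primary outcome is available". It makes no exception for Test Valley.

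**The concern.** The protocol offers one figure for the sensitivity of its main test, and that figure belongs to a larger set of households than the main test will use. The 1,600-household figure now fits only the treatment-only sensitivity analysis that includes Test Valley.

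This matters most if the result is null. Section 3.2 sets out how a null would be interpreted: either the calls did not raise engagement, or the services did not work. A reader weighing those explanations will first ask what size of effect the trial could have detected. Taking 7pp as detectable with 80% power would make a null look more informative than it is.

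Sections 5.2 and 10.1 also define the primary set differently, and the pre-specified analysis population should be beyond argument before outcomes are seen.

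**Working it through.** **Inputs, all from the protocol.** Alpha 0.05 and power 0.80 (section 9.1); two-sided (Table 7); equal allocation (section 5.2); 500 households per LA and 20% attrition (section 9.2); covariates assumed to explain no outcome variance (section 9.1); base rate of 50% or more expected (footnote to Figure 3).

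**Sample sizes.**
- Scenario C: 4 × 500 = 2,000 randomised; × 0.8 = 1,600 analysed; 800 per arm. This matches Table 7.
- Primary analysis under version 3.0: 3 × 500 = 1,500 randomised; × 0.8 = 1,200 analysed; 600 per arm.

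**Formula.** Two-proportion normal approximation with control rate p, treated rate q = p − d, mean rate m = (p + q)/2 and n per arm. The MDES is the d that solves

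d = 1.96 × √(2m(1−m)/n) + 0.8416 × √((p(1−p) + q(1−q))/n).

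**Reproducing the plan at p = 0.50.** For Scenario C, n = 800: 0.0489 + 0.0209 = 0.0698, or 6.98pp. The same calculation gives 6.25pp for A (1,000 per arm), 6.70pp for B (868), 7.49pp for D (694), and 5.74pp for A with 5% attrition (1,187). Rounded up, these are 7, 7, 8 and 6, with 7 for C, which are the stated upper ends. Table 7 is right for the numbers it uses.

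**Three LAs at p = 0.50.** With n = 600: 0.0564 + 0.0241 = 0.0805, or 8.05pp. This is about 15% larger than Scenario C, as √(800/600) = 1.155 implies.

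**Power for a 7pp reduction, 50% to 43%.** Here m = 0.465.
- n = 800: (0.07 − 0.0489)/0.0249 = 0.85, giving 80%.
- n = 600: (0.07 − 0.0564)/0.0287 = 0.47, giving 68%.

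**MDES (pp) for a reduction, by base rate, at 20% attrition.**

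| Base rate | Scenario C, 800 per arm | Three LAs, 600 per arm |
|---|---|---|
| 50% | 6.98 | 8.05 |
| 60% | 6.94 | 8.02 |
| 70% | 6.60 | 7.64 |
| 80% | 5.89 | 6.84 |
| 90% | 4.60 | 5.38 |

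**Other assumptions for three LAs at 50%.**
- 5% attrition (712 per arm): 7.40pp.
- No attrition (750 per arm): 7.21pp.
- 20% attrition plus the 20% cut to Batches 2 and 3 used in Scenarios B and D (about 520 per arm): 8.65pp.

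**The case against.** The best reply is that section 9 is dated planning. It says the calculations preceded the final list of councils, and it ties Scenario C to first registration. The sample was set by LA capacity, not derived from an MDES, so restating the figure changes no household, model or estimate. The 8pp figure also takes the least favourable base rate, no covariate gain (which the protocol itself calls unlikely) and an attrition figure it calls conservative. A null will in any case be read from the confidence interval.

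Part of this stands. The consequence is for reporting, not conduct. The 8pp figure is an upper value within the 50–90% range. At 5% attrition the three-LA set would be 1,425, larger than Scenario D, so it is smaller than every listed scenario only at the attrition the plan adopts. But section 9 is current text in version 3.0, whose revision note says that the implications for analysis are outlined, and the power implication is not. The other assumptions are the plan's own, and with no attrition at all the MDES at 50% still exceeds 7pp.

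Four stronger readings are tempting and not supported:
- **That Table 7 contains an arithmetic error.** It reproduces for four LAs.
- **That about 2,000 in Table 1 is wrong.** It is the target number of participants, and Test Valley is still randomised.
- **That the economic evaluation divides four-LA costs by a three-LA effect and so overstates cost per household helped.** Section 12.3 says cost estimates "will be scaled up in line with the project target population in each LA to represent the whole project", but nothing says that beneficiary households will be counted in three LAs only. Section 12.4 takes the impact estimate together with a relevant population size, which may be the same population as the costs.
- **That the 2pp lower end misleads.** Section 9.1 says the range varies with the base rate and that little is known about how well the scores predict, and the 50% expectation is conditional on the model working.

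**Conclusion.** The point holds as a failure to update. On 500 households per LA, 20% attrition and no covariate gain, the primary analysis has 1,200 households. Its MDES exceeds the stated upper end of 7pp at base rates of about 50–70% and lies within the stated range at 80% and above. At every base rate from 50% to 90% it is about 15–17% larger than Scenario C's. Lower attrition narrows the gap at a 50% base rate without closing it. Covariate gain could narrow it further, but the plan claims none.

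On the analysis population, the specific exclusion in section 5.2 plainly governs, so the intended primary set is not in real doubt. Section 10.1 is nevertheless wrong as it stands.

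**What to change.** 1. Add a three-LA scenario to Table 7: 1,500 randomised, 1,200 analysed, MDES about 8pp at a 50% base rate.
2. In section 9.1, restate the MDES for the primary analysis as about 8pp at 50%, falling to about 5.4pp at 90%. Say that Scenario C now describes only the treatment-only analysis that includes Test Valley.
3. In section 10.1, define the analytic sample for the primary and secondary analyses as households with the outcome in the three risk-scored LAs, and point to section 5.2.
4. Leave about 2,000 in Table 1, with a note that about 1,500 of those randomised enter the primary analysis before attrition.

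The cost is one re-run of the power calculation and a few lines of text, and the stated sensitivity becomes less favourable. Version 3.0 is dated 18 December 2025 and the primary outcome pulls are scheduled for February to April 2026, so on that schedule the change could be made before primary outcomes are seen.
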